CFR	Code of Federal Regulation
CI	Confidence Interval
CMR	Cardiac Magnetic Resonance
CRF	Case Report Form
CRM	Clinical Research Manager
CRO	Contract Research Organization
CTR	Clinical Trial Report
DICOM	Digital Imaging and Communications in Medicine
DPPG.Na	Dipalmitoyl phosphatidylglycerol sodium
DSPC	Distearoylphosphatidylcholine
EBD	Endocardial Border Delineation
ECG	Electrocardiogram
F°	Farenheit
FDA	Food and Drug Administration
GCP	Good Clinical Practice
GC-MS	Gas Chromatography-Mass Spectrophotometry
GGT	Gamma-Glutamyl Transpeptidase
h	Hour
HLHS	Hypoplastic Left Heart Syndrome
IB	Investigator's Brochure
ICH	International Conference on Harmonization
IND	Investigational New Drug
IP	Investigational Product
IRB	Institutional Review Board
ITD	Intention to Diagnose
Kg	Kilogram
LDH	Lactic Acid Dehydrogenase
LV	Left Ventricle / Left Ventricular
LV EBD	Left Ventricular Endocardial Border Delineation
LVEF	Left Ventricular Ejection Fraction

MedDRA	Medical Dictionary for Regulatory Activities
mg	Milligram
MI	Mechanical Index
min	Minute
ml	Milliliter
ng	Nanogram
PEG	Polyethylene Glycol
PT	Prothrombin Time
QRS	Q-wave — depolarization of the ventricular septum R-wave — activation of most of the ventricle S-wave — last stage of ventricular depolarization
QT	measure of the time between the start of the Q wave and the end of the T wave in the heart's electrical cycle
QTc	QT corrected for heart rate
RBC	Red Blood cell Count (total erythrocyte count)
ROW	Rest of the World
RR	Time between beats used to calculate heart rate
SAER	Serious Adverse Event Report
SAP	Statistical Analysis Plan
SAS	Statistical Analysis Software
SF ₆	Sulfur hexafluoride
SGOT	Serum Glutamic Oxaloacetic Transaminase
SGPT	Serum Glutamic Pyruvic Transaminase
SUSAR	Suspected Unexpected Serious Adverse Reaction
TOF	Tetralogy of Fallot
2D	Two dimensional
WBC	White Blood Cell Count (total leukocyte count)
WHO	World Health Organization
UEUS	Unenhanced Ultrasound
ul	Microliter
USA	United States of America
VSD	Ventricular Septal Defect
w/v	Weight/ Volume
w/w	Weight/ Weight
βHCG	Beta Human Chorionic Gonadotropin

1 Title of Study

A MULTICENTER CLINICAL EVALUATION OF SAFETY AND EFFICACY OF LUMASON™ AS A CONTRAST AGENT IN PEDIATRIC ECHOCARDIOGRAPHY

2 Protocol Number

This study is being conducted under protocol number: BR1-140.
IND number: 46,958.

3 Introduction

Echocardiography has become the primary imaging tool in the diagnosis and assessment of congenital and acquired heart disease in children and adolescents.¹ Even though technically challenging echocardiographic windows are a more common challenge in adults, there is also a similar subset of children who do have limited, technically suboptimal echocardiographic windows secondary to obesity, congenital heart disease, chest wall abnormalities or prior surgical interventions resulting in suboptimal echocardiograms.²

Clinical trials have shown that suboptimal echocardiograms defined as non-visualization of at least 2 or more contiguous segments in the standard echocardiographic views³ can be converted to a diagnostic study with the use of contrast in 75% to 90% of patients with fundamental and harmonic imaging modalities used.⁴⁻⁸ For more than a decade, intravenous contrast echocardiography has been demonstrated to be a very useful tool in optimizing endocardial border delineation (EBD) in the adult population.⁹⁻¹⁶ Ultrasound contrast is not approved by the Food and Drug Administration (FDA) for use during pediatric echocardiography because the safety and efficacy of contrast agents have not been established definitively in children.¹⁷ Although the reported clinical use of transpulmonary contrast agents in the pediatric population is limited, the utility of these agents in pediatric population can be quite valuable.^{18,19} Contrary to general belief, children do not always have diagnostic echocardiographic studies. Furthermore, dealing with children, especially sick children, presents a unique challenge. Children are frequently frightened and need coaxing and distractions to cooperate with the study. In addition, pediatric cardiologists have less training in regional wall-motion interpretation during stress echocardiography than their counterparts in adult cardiology.¹⁷ These factors make contrast agents valuable in evaluating pediatric patients, particularly those who routinely undergo serial echocardiographic studies including stress echocardiograms (such as patients with Kawasaki disease,²⁰ those who have undergone the arterial switch operation, other coronary reimplantation surgery or cardiac transplantation), because contrast agents facilitate EBD.^{17, 18, 19, 21}

Congenital heart defects are serious and common conditions that have significant impact on morbidity, mortality, and healthcare costs in children. The most commonly reported incidence of congenital heart disease is between 4 and 10 per 1000, averaging 8 per 1000 live births. An

estimated minimum of 32,000 infants are expected to be affected each year in the United States of America (USA). Of those, an approximate 25%, or 2.4 per 1000 live births require invasive treatment in the first year of life. Furthermore, congenital cardiovascular defects are the most common cause of infant death resulting from birth defects; >24% of infants who die of a birth defect have a heart defect. The 2008 death rate attributable to congenital cardiovascular defects was 1.1. Infant mortality rates under one year of age were ranging from 34.9 to 46.5.²² Congenital heart defects range in severity from small holes between chambers that may resolve spontaneously to major malformations that can require multiple surgical procedures before school age and may result in death in infancy or in childhood. The most common complex defects include Tetralogy of Fallot (TOF), Transposition of the great arteries (TGA), atrial and ventricular septal defects (ASD/VSD), Coarctation of the aorta, Hypoplastic left heart syndrome (HLHS).²² In children born with complex congenital heart disease, functional evaluation of the ventricle is often necessary and becomes challenging.¹⁷ Poor acoustic windows in pediatric population often limit transthoracic images particularly for those have undergone surgical repair. Ultrasound contrast agents can be helpful in EBD of these geometrically unusual chambers, thereby aiding in functional assessment. These pediatric population groups include patients after procedures to repair TOF and after the Senning and Mustard procedures.^{17, 18, 19, 21} The growing population of patients with congenital heart disease has led to a markedly increased use of non-invasive cardiac imaging in their care.²³ These patients often have residual structural and hemodynamic abnormalities, which necessitate serial comprehensive assessment, but transthoracic echocardiography is often challenging due to acoustic window limitations secondary to previous cardiac operations, implanted pacemaker leads, and alterations in the geometry due to shunts and baffles. Furthermore, these patients undergo cardiac magnetic resonance (CMR) imaging due to limitation of echo without contrast enhancement, if they do not have pacemaker, but the artifacts produced by implanted metal prevent assessment of imaging of cardiac structures within several centimeters of the stainless coils which are often used to occlude undesirable collateral vessels.²⁴

In a recently published study,²¹ efficacy of ultrasound contrast both at rest and stress has been prospectively studied in 51 patients with congenital heart disease some of which were children. Results of this particular study indicated that ultrasound contrast at rest and stress echo enabled safe and comprehensive assessment of anatomy and biventricular function by improving EBD in all patients with an increased number of wall segments visualized.²¹

Similarly, McMahon et al¹⁹ demonstrated the safety of using contrast echocardiography in 20 children ranging in age from 9 to 18 for the evaluation of congenital heart disease, or cardiac function in children with arrhythmia or undergoing chemotherapy. Significant improvement in border delineation in all myocardial segments with the concomitant use of contrast and harmonic imaging has been reported. More importantly, significant reduction in interobserver variability of ejection fraction using harmonic imaging and contrast echocardiography versus fundamental or harmonic imaging alone without contrast was shown.¹⁹ McMahon et al provided further evidence that the use of contrast agents is safe, improves accuracy of evaluation of cardiac function, and helps to better delineate the endocardial border of specific segments in children.¹⁹ Given the ever increasing demand for acquisition of high quality echocardiographic data in children with cardiac

problems, contrast echocardiography plays an important role as a useful non-invasive diagnostic tool in obtaining accurate evaluation of anatomic and functional assessment.¹⁹

McMahon et al studied series of 70 children with a median age of 10.3 with suboptimal echocardiographic windows. The use of harmonic imaging and fundamental imaging without contrast usage has been compared. Scores for harmonic imaging were significantly higher for all views in comparison to fundamental imaging in children.² The improvement of the image quality obtained with harmonic imaging in children² is similar to the results of studies in adults.^{13, 25-28}

Recent studies indicate that contrast enhanced two dimensional (2D) echocardiography with harmonic imaging had excellent correlation with radionuclide, magnetic resonance and computed tomographic measurements of Left ventricular (LV) volumes and left ventricle ejection fraction (LVEF) with improved interobserver agreement and physician interpretation confidence compared to unenhanced harmonic imaging in adult population.^{29, 30} Furthermore, increasing accuracy of LVEF measurements have been associated with contrast-enhanced harmonic imaging over unenhanced harmonic imaging and fundamental imaging, respectively.^{31,32}

Due to the increased use of transthoracic echocardiography as a non-invasive cardiac imaging tool in children and an increasing number of suboptimal, non-diagnostic quality studies mostly due to previous cardiac operations and alterations to cardiac anatomy especially in congenital heart disease patients, we aim to study the safety and efficacy of Lumason™ (sulfur hexafluoride lipid-type A microspheres) for injectable suspension in children 9-17 years with suboptimal images undergoing resting transthoracic echocardiogram with harmonic imaging modality. Lumason™ (under the trade name SonoVue®) is approved for use in echocardiography both at rest and stress in the European Union (EU) for use in the adult population. No Ultrasound Contrast Agent is currently approved in the pediatric population for use in rest echocardiography to improve LV EBD in patients with suboptimal unenhanced imaging.

4 Study Objectives

Primary Objective:

- To assess the efficacy of LUMASON enhanced transthoracic echocardiography [CEUS] in pediatric subjects with suboptimal Left Ventricular Endocardial Border Delineation (LV EBD) at unenhanced transthoracic echocardiography [UEUS] in terms of:
 - Change from baseline [UEUS] versus [CEUS] in total LV EBD score.
 - Proportion of subjects with adequate LV opacification

Secondary Objective:

- To obtain safety data in pediatric subjects administered LUMASON for LV EBD improvement during echocardiography.
- To obtain pharmacokinetic data in a subset of pediatric subjects undergoing analysis of SF₆ concentration in blood.

5 Investigational Plan

5.1 Overall Study Design Description

This is a Phase III multicenter, open-label study that will be conducted at approximately 7-12 sites in the United States in pediatric subjects with suboptimal LV EBD on non-contrast 2D transthoracic echocardiography with harmonic imaging within 30 days of the LUMASON administration. It is estimated that 92 subjects will be enrolled to provide 73 evaluable subjects.

Three cardiologists unaffiliated with enrolling centers (blinded readers), blinded to the subject's identity and clinical profile will independently evaluate the echocardiograms. The efficacy analysis will be primarily based on the blinded reader evaluations.

Imaging conditions will be representative of those used in routine clinical practice and will include LV EBD with harmonic imaging modality.

One or two of the sites participating in this study will also be requested to consent a subset of subjects for additional blood sampling for analysis of SF₆ concentration (Pharmacokinetic subset) in blood from a total of 6 subjects (3 males and 3 females) in the age group 9 up to 12 years of age and 6 subjects (3 males and 3 females) in the age of >12 up to and including 17 years.

5.2 Discussion of Study Design

The current study is designed to assess the efficacy of LUMASON enhanced echocardiography vs. unenhanced echocardiographic imaging in pediatric population (age 9 to 17 years) with suboptimal images and assess the proportion of subjects with "adequate" LV opacification. The subjects to be enrolled in the current study are representatives of those who could benefit most from contrast-enhanced echocardiography.

Echocardiography has become the primary and ideal tool for cardiac assessment and serial follow up of ventricular size and function as it is non-invasive, portable and efficacious in providing detailed anatomic, hemodynamic and physiologic information about the pediatric heart.² There has been an increasing number of sub-optimal, non-diagnostic quality studies mostly due to previous cardiac operations and alterations to cardiac anatomy due to shunts and baffles especially in congenital heart disease patients, which necessitate serial comprehensive assessment of their residual structural and hemodynamic abnormalities.^{1, 3, 17, 21, 23}

The current guidelines of American Heart Association (AHA)³ and American Society of Echocardiography (ASE)¹⁷ suggest application for ultrasound contrast use in difficult to image patients with suboptimal image quality at their presenting rest echocardiography exams. Both guidelines define suboptimal studies when two contiguous segments are not visualized in any three of the apical views. The same criteria will be applied in children and representative of those used in routine clinical practice and will include assessment of LV EBD using harmonic imaging modality. Commercially available echocardiographic equipment and transducers will be used for all patients. Patients must have undergone a previous transthoracic echocardiogram with harmonic imaging modality within the one month period prior to enrollment resulting in suboptimal LV EBD in order to be included in the study. Subjects who are enrolled in the study

will then undergo a pre-injection (baseline) echocardiogram with the standard apical 4-, 2-, and 3-chamber views obtained with harmonic imaging. A recording of 2D transthoracic harmonic echocardiography images will be performed from 30 seconds prior to injection of LUMASON and then continue until all contrast enhanced images are acquired.

The first primary efficacy endpoint of LUMASON studies (change from baseline in total of LV EBD score) is the one prospectively defined and agreed upon with the FDA for the adult studies.

A LV 17-segment model will be utilized as recommended by ASE guidelines.^{17,3} The standard views of a 2D echocardiogram as defined by the ASE are all used as part of pediatric echocardiogram.^{1,17} The clinical utility of improvement in LV EBD resulting from opacification of LV as an aid in determination of more clinically relevant parameters is recognized by the 2008 ASE consensus statement as leading to improvement in feasibility, accuracy, and reproducibility of echocardiography for the qualitative and quantitative assessment of LV structure and function.¹⁷

The co-primary efficacy endpoint (adequacy of LV opacification following injection) will be graded according to the 4-point rating scale (see section 7.7). Useful appearance of contrast within the LV including ventricular opacification rating of +2 (non-homogeneous) or +3 (complete and homogeneous) will be considered as adequate LV opacification.

A subset of 12 subjects is considered to be sufficient for the estimation of the pharmacokinetic parameters, based on the findings of a prior study in healthy adult subjects.³³

In adults, the dose for LV opacification is a fixed dose of 2 mL. Assuming a notional adult body weight of 70 kg, this represents a dose of 0.03 mL/kg body weight. This dose will be used for the study in pediatric population.

Most or all of contrast agent dose rapidly dissolves in the blood and subsequently eliminates by the lungs. The cumulative recovery of SF₆ in expired air averaged 86% to 94% of the administered dose in healthy subjects.³³ The results of this study published by Morel et al³⁶ had shown that LUMASON rapidly removed from the blood by the pulmonary route with 40% to 50% of the injected dose eliminated within the first minute after administration and 80% to 90% eliminated by 11 minutes after administration. Furthermore, the recovery of SF₆ in expired air in subjects with impaired lungs averaged 102%.³⁴ This finding indicates that the patients eliminate all of the SF₆ from LUMASON via their lungs rather than an alternate elimination route, despite the impairment of lung function. Most alveolar maturation occurs in the first 2 years of life, so that no differences in the elimination of the gas between adults and pediatric patients 9-17 years-old should be expected.³⁵ No studies ever reported the use of ultrasound contrast agents during rest echocardiography in patients below 9 years of age.

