5.2.1 Risk-Benefit Considerations

A benefit from contrast-enhanced LV EBD resulting in improved³⁶ diagnostic quality of echocardiographic examinations should be expected. Given the fact that the subjects to be enrolled in the present clinical trial will be already scheduled for echocardiographic examination but with suboptimal images and have no evidence of intracardiac shunts, inclusion in the study is not likely to add any risk for the subjects, since no particular safety concerns can be expected.

when administering LUMASON to children with respect to the safety profile of LUMASON. Furthermore, contrast enhanced transthoracic echocardiogram supposed to prevent the risk of those subjects being exposed to radiation through other imaging modalities in the downstreaming of appropriate assessment of cardiac structures.

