5.4.1 Inclusion Criteria

Enroll a subject in the study if they meet the following inclusion criteria:

- Is male or female, 9 to 17 years of age;
- Written informed consent is obtained from the subject's parent(s) or legal acceptable representative(s) (according to local regulations);
- Assent from the subject is obtained when applicable, that is, when it is required according to local regulations (IRB requirements) (see section 10.2);
- Is suspected of having cardiac disease or undergoing evaluation of cardiac anatomy for congenital heart disease;
- Has undergone a previous transthoracic echocardiogram within a one month period prior to enrollment in this study resulting in suboptimal LV EBD defined as ≥ 2 contiguous segments in any given view that cannot be visualized.

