6.5 Administration

Once reconstituted, LUMASON will be administered intravenously as a single 0.03 mL/kg bolus injection during echocardiography. The LUMASON injection will be followed immediately with 5 mL of saline to flush the intravenous line of any remaining contrast agent.

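### The 0.03 mL/kg rule passes the fixed 2 mL adult dose it was derived from above about 66.7 kg, and the rationale does not address those volumes

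*Combined protocol and SAP*

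**What the plan says.** The dose rationale is in section 5.2. It gives the adult reference as a fixed volume: "In adults, the dose for LV opacification is a fixed dose of 2 mL". It then converts that volume to a per-kilogram figure: "Assuming a notional adult body weight of 70 kg, this represents a dose of 0.03 mL/kg body weight". The per-kilogram figure is carried over: "This dose will be used for the study in pediatric population".

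Section 6.5 is the operative instruction: "LUMASON will be administered intravenously as a single 0.03 mL/kg bolus injection during echocardiography". It states no maximum volume and does not refer back to the 2 mL figure.

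Eligibility in section 5.4.1 runs across adolescence ("Is male or female, 9 to 17 years of age"). Neither 5.4.1 nor 5.4.2 sets a limit on weight or BMI. The Introduction (section 3) attributes poor images in some children to "limited, technically suboptimal echocardiographic windows secondary to obesity, congenital heart disease, chest wall abnormalities or prior surgical interventions".

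The risk-benefit text in 5.2.1 rests on the safety profile of the product and says that "no particular safety concerns can be expected". Section 8.2 requires accidental overdose and wrong-dose errors to be reported within 24 hours. Section 9.4 summarises administered volume and lists dosing by subject. Section 9.5 summarises adverse events by class, term, intensity and causality, but not by volume received.

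**The concern.** A fixed dose does not depend on body weight; a per-kilogram dose rises with it without limit. The two agree at only one weight. Section 5.2 moves from the first to the second through a single notional weight and does not say what should follow for subjects heavier than that. On the protocol's own description, a 100 kg adult would receive 2 mL, while a 17-year-old of the same weight in this trial would receive 3.0 mL.

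Three things are at stake:

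- **The safety argument.** The only adult volume for LV opacification that the documents give is 2 mL. For subjects who receive more, the reliance in 5.2.1 on the existing safety profile needs a stated basis. Section 5.2 also argues that children aged 9 to 17 should eliminate the gas as adults do, but that argument does not deal with a volume above 2 mL.
- **Safety reporting.** The text gives a fixed adult volume in one place and an open-ended per-kilogram rule in another. It would help sites to know which is the reference when they judge an overdose under 8.2.
- **Interpretation.** Safety data in children are a stated objective. As planned, the tables would not show whether any adverse events arose in subjects who received more than the adult volume.

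**Working it through.** **Inputs**

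- Adult reference dose: 2 mL, fixed (5.2).
- Conversion weight: 70 kg, notional (5.2).
- Pediatric rule: 0.03 mL/kg, single bolus (5.2 and 6.5).
- Reconstituted volume: 5 mL of saline per vial (6.4).

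The documents give no weight distribution. The weights in the table below are therefore illustrative assumptions.

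**Step 1: reproduce the plan's figure.** 2 mL / 70 kg = 0.0286 mL/kg, which rounds to 0.03 at two decimals. The stated figure is reproduced. The rounding is upward by 0.03 / 0.0286 = 1.05, or 5%.

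**Step 2: put the anchor weight back in.** 0.03 × 70 = 2.1 mL, not the 2 mL from which the rule came.

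**Step 3: find the crossover.** 2 / 0.03 = 66.7 kg. With the unrounded 2/70, the crossover would be 70 kg. Between 66.7 and 70 kg, then, the excess is wholly a rounding effect.

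**Step 4: volume by weight.** The written rule is 0.03 × weight; the unrounded rule is (2/70) × weight.

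| Weight (kg) | Written rule (mL) | Relative to 2 mL | Unrounded rule (mL) |
|---|---|---|---|
| 50 | 1.5 | −25% | 1.43 |
| 60 | 1.8 | −10% | 1.71 |
| 70 | 2.1 | +5% | 2.00 |
| 80 | 2.4 | +20% | 2.29 |
| 100 | 3.0 | +50% | 2.86 |
| 120 | 3.6 | +80% | 3.43 |

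Above 70 kg most of the excess comes from scaling a fixed dose linearly with weight, not from rounding. At 100 kg, for example, the unrounded rule would already give 2.86 mL.

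**Step 5: look for another limit in the text.** None is stated. Taking 5 mL as the volume in one vial, the vial would not bind until 5 / 0.03 = 167 kg.

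This point does not touch the sample size or the power calculation.

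**The case against.** The strongest reply is that the sections do not conflict. What 5.2 carries over is the per-kilogram figure, and 6.5 orders exactly that figure. The 70 kg is openly called notional, and 2 mL is described as the adult dose, never as a ceiling. All of this stands. A reader might infer that 5.2 and 6.5 order different doses, or that 6.5 breaks a stated limit; the documents support neither reading. What remains is that the rule exceeds the dose cited as its basis and the text does not say so.

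A second reply is that the affected group may be small. Obesity appears once, in a list of causes in the Introduction. Sections 3 and 5.2 attribute poor studies mostly to previous surgery and altered anatomy, and entry requires suspected cardiac disease or evaluation for congenital heart disease. This also stands. Heavier adolescents are foreseeable in a trial that enrols up to age 17, but the documents do not show that they are a central part of it.

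A third reply is that the safety profile cited in 5.2.1 is set out in the Investigator's Brochure and in other trial reports, which may cover larger volumes. That is possible, and those sources are not available here. A reader might infer that volumes above 2 mL are unsafe or untested; the documents do not show either. If the Brochure does cover them, the sponsor can meet the safety part of this point by citing it.

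Finally, weight and BMI are already summarised (9.1), and volume is summarised and dosing listed by subject (9.4), so the subjects concerned could be identified without an amendment. That is true of the data and is why the listing costs little. It does not supply the missing rationale.

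**Conclusion.** The point holds as a gap between the dosing rule and its stated adult basis. Followed as written, 0.03 mL/kg gives more than the fixed adult dose to every subject above about 66.7 kg. The excess is at most 5% up to 70 kg, 20% at 80 kg and 50% at 100 kg. No passage acknowledges or justifies this.

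The arithmetic uses only figures in the protocol. That there is no maximum volume and no weight limit on entry is read from 5.4.1, 5.4.2 and 6.5. How many subjects would be affected is unknown, because no weight distribution is given. No conclusion is drawn about the safety of volumes above 2 mL, about an effect on either co-primary endpoint, or about the consent form, whose text was not available. The matter should be settled because it concerns dosing in a pediatric trial with a safety objective, and settling it is cheap.

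**What to change.** Before the first subject is dosed:

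1. Reconcile 5.2, 5.2.1 and 6.5 so that the rule and its stated adult basis agree for subjects above the crossover weight, and cite the safety basis for whatever is intended. Which volume is right is for the sponsor's clinicians; no view is taken here.
2. In 8.2, use the same reference when defining accidental overdose, so that sites judge it consistently.
3. In 9.5, add a listing of adverse events for any subject who received more than 2 mL, showing weight and volume.

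The cost is a short protocol amendment and one listing. Weight and administered volume are already collected, so no extra subjects, procedures or data are needed.
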